6.1 Efficacy Assessments

Note: Efficacy questionnaire questions will be asked “with reference to study knee” i.e. to obtain scores specific for the treated knee.

6.1.1 WOMAC® Osteoarthritis Index ([Bellamy 1988](#))

The clinical effects of treatment on OA pain and function will be evaluated during clinic visits at 6, 12, and 24 weeks, and telephone contacts at 2, 4, 8 and 10 weeks, using the WOMAC Index

3.1, and the PGA. All patients are required to take at least five minutes to complete the questionnaire.

Patients are asked about their pain, stiffness, and function in the knee (study joint) due to arthritis during the last 24 hours.

In addition to WOMAC scoring during clinic visits, daily WOMAC A pain sub scores will be collected for seven days up to and including Baseline and Week 12 to allow for calculation of WOMAC A weekly pain scores, which will be used for conducting the primary efficacy analysis.

Patients respond to each subscale by using a 5-point adjectival Likert score (0 = None, 1 = Mild, 2 = Moderate, 3 = Severe, 4 = Extreme) and 100mm VAS.

The WOMAC B and WOMAC C sub scores will be collected at Weeks 0 (Baseline), 2, 4, 6, 8, 10, 12, and 24 using the 5-point Likert scale. Patients respond to each subscale by using a 5-point adjectival Likert score (0 = None, 1 = Mild, 2 = Moderate, 3 = Severe, 4 = Extreme).

6.1.2 Patient's Global Assessment of Disease Severity (PGA)

The PGA should be completed by patients at Screening, pre-dose Day 1 (prior to injection), and at Weeks 2, 4, 6, 8, 10, 12 and 24.

Patients are asked the following question: "Considering all the ways in which your arthritis affects you, please indicate how you are doing."

Patients respond by using a 5-point adjectival Likert score (0 = Very Well, 1 = Well, 2 = Fair, 3 = Poor, 4 = Very Poor).

6.2 Safety Parameters

Based on results of a Phase 1b and a Phase 2 randomized, controlled, repeat-blind study of a single IA injection of Ampion < 5 kDa ultrafiltrate of 5% HSA in adults with OAK (AIK study), in which no clinically significant differences between active and placebo were found in either electrocardiogram or blood parameters, safety will be assessed by recording adverse events, vital signs, results of physical examination, and by recording prior and concomitant medications.

6.2.1 Vital Signs

Vital signs (radial pulse rate, SBP, DBP, and body temperature) should be recorded at Screening, pre- and post-treatment Day 1, and then on visits at Weeks 6, 12 and 24.

Vital signs should be taken after the patient has rested in a seated position for at least five minutes.

Table 6.1 Schedule of Assessments and Procedures

	Screening	Pre-Baseline (phone)	Baseline	24-hours (phone)	Week 2 (phone)	Week 4 (phone)	Week 6	Week 8 (phone)	Week 10 (phone)	Pre-Week 12 (phone)	Week 12	Week 24	Early Term.
Assessments & Procedures	Visit -1 Day-28 to 0	Visit 0 Day -6 to 0	Visit 1 Day 0	Visit 2 Day 1	Visit 3 Day 14 ± 7	Visit 4 Day 28 ± 7	Visit 5 Day 42 ± 7	Visit 6 Day 56 ± 7	Visit 7 Day 70 ± 7	Visit 8 Day 77 ± 7	Visit 9 Day 84 ± 7	Visit 10 Day 174 ± 7	
Informed Consent	X												
Inclusion/exclusion criteria	X		X										
Medical history/prior medications	X		X										
Concomitant medications	X		X	X	X	X	X	X	X		X	X	X
Urine sample			X**								X		
Physical examination	X		X				X				X	X	X
Vital Signs	X		X				X				X	X	X
Randomization			X										
Review Diary Completion Instructions	X								X				
Phone Contact Daily Collection Reminder		X								X			
WOMAC A (Likert)	X	X*	X***		X	X	X	X	X	X*	X***	X	X
WOMAC A (VAS)	X	X*	X***							X*	X***		X
WOMAC B and C (Likert)	X		X		X	X	X	X			X	X	X
PGA	X		X		X	X	X	X			X	X	X
X-ray ¹	X												
Study treatment			X										
Dispense Rescue medication			X										
Review Rescue medication				X	X	X	X	X	X		X	X	X
Adverse Events			X	X	X	X	X	X	X		X	X	X

Visits are in clinic except for Day 1 and Weeks 2, 4, 8 and 10 when patients will be contacted by telephone

¹X-ray may be acquired at Screening to satisfy inclusion criteria, “Index knee must be symptomatic for greater than six months with a clinical diagnosis of OA and supported by radiological evidence (KL 4) that is not older than six months prior to the date of screening”.

*Patients will complete 7 daily pain score assessments up to and including the Baseline and Week 12 visits to allow calculation of WOMAC A weekly pain scores. The Screening and first Pre-Baseline daily pain score collection may occur on the same day, in office or at home, as appropriate.

**Urine will only be collected at Baseline if necessary to conduct a pregnancy test; collection to occur as applicable

***The WOMAC may occur in office or at home, and may serve as the 7th WOMAC Daily Pain collection

7 DISCONTINUATION CRITERIA

7.1 Early Discontinuation of the Study

It is agreed that for reasonable cause, either the investigator or the Sponsor may terminate this study, provided a written notice is submitted at a reasonable time in advance of intended termination; if by the investigator notice is to be submitted to Ampio Pharmaceuticals, Inc., and if by the Sponsor, notice will be provided to each investigator.

If a severe local reaction or drug-related SAE occurs at any time during the study, the Safety Monitoring Committee will review the case immediately.

The study will be immediately suspended and no additional Ampion treatments administered pending review and discussion of all appropriate study data by the SMC if one or more patients develop any of the following adverse events deemed to be possibly, probably, or definitely related to Ampion by the Investigator and/or Medical Monitor, based upon close temporal relationship or other factors:

- Death
- Anaphylaxis (angioedema, hypotension, shock, bronchospasm, hypoxia, or respiratory distress) Induction of autoimmune arthritis
- Hepatic failure
- Aplastic anemia

The study will not be restarted until all parties have agreed to the course of action to be taken and the IRB/EC has been notified.

7.2 Early Discontinuation of Individual Patients

Patients are to be withdrawn from the study for any of the following reasons:

- Withdrawal of informed consent
- Patient is lost to follow-up

Patients will also be withdrawn at any time if the investigator concludes that it would be in the patient's best interest for any reason. Protocol violations do not lead to patient withdrawal unless they constitute a significant risk to the patient's safety.

Patients can voluntarily withdraw from the trial for any reason at any time. They are to be considered withdrawn if they state an intention to withdraw, fail to return for visits, or become lost to follow up for any reason. Patients withdrawing from the study because of an AE should be followed for at least 30 days, resolution of the AE or until no further improvement is expected, whichever comes first.

8 TREATMENT

Eligible patients will receive a single IA injection into one knee of either Ampion or a saline injection, dependent on study arm.

Patients will be allocated to a treatment in accordance with the randomization schedule following confirmation of eligibility before treatment.

8.1 Dosing and administration of study medication

Appropriately trained site personnel should administer the study treatment.

If both knees are osteoarthritic, then the Investigator at Screening should select the knee that best satisfies the requirements for the study (see inclusion criteria) as the study knee. The study knee should be treated in accordance with the randomization schedule.

It is recommended that the study treatment be administered into the knee joint space under sterile prep conditions (i.e. the knee should be cleaned with an antiseptic). The treatment area may be anesthetized with local anesthesia including a topical anesthesia, injection of lidocaine, or nothing, as determined by the Principal Investigator. The recommended needle of choice for this procedure is a 25-gauge needle that is 1.5 inches long. The needle may be passed obliquely towards the trochlear groove. If an effusion is present, aspiration should not be performed, and the effusion should be noted in the study source notes/eCRF. Injection should proceed easily. Failure to easily inject should be documented. The same sized needle should be used for both Ampion and saline administration and recorded in the study source notes/eCRF. The date of administration should be recorded in the study source notes/eCRF.

8.2 Drug Storage and Accountability

Study drug should be stored at controlled room temperature (59° – 77°F or 15° – 25°C). Each site shipment of study drug will include temperature monitors and instructions to download the temperature data to Ampio Pharmaceuticals, Inc. If the study drug is stored at the clinical site, temperature should be monitored at least daily until use to ensure storage at the defined temperature.

The Investigator, the clinical site pharmacist, or other personnel authorized to store and dispense investigational product is responsible for ensuring that the investigational product used in the clinical study is securely maintained as specified by the Sponsor and in accordance with the applicable regulatory requirements.

All investigational product is to be dispensed in accordance with the Investigator's prescription and it is the Investigator's responsibility to ensure that an accurate record is maintained of investigational product issued and returned.

If any quality issue is noticed upon the receipt or use of an investigational product (i.e. deficiencies in condition, packaging, appearance, associated documentation, labeling, etc.), Ampio Pharmaceuticals, Inc. must be promptly notified.

Under no circumstances may the Investigator supply investigational product to a third party, allow the investigational product to be used other than as directed by this clinical study protocol, or dispose of investigational product in any other manner.

Ampio, or designated representative, will instruct sites on study kit returns and/or destruction of study drug. If returned, study kits must be returned to Ampio Pharmaceuticals, Inc., or designated representative after study completion.

8.3 Concomitant Treatments and Rescue Medication

The following medications / therapies are NOT allowed during this clinical study:

1. No IA injected pain medications in the study knee during the study.
2. No analgesics containing opioids.
3. No NSAID use during the 48 hours prior to efficacy evaluations.
4. No clinically significant increase in NSAID use above baseline/pre-study dosing levels to treat worsened symptoms in the treated knee.
 - a. NSAID use during the study may be continued at baseline/pre-study dosing levels and may be increased or decreased if clinically indicated; acetaminophen is also available as a rescue medication during the study from the provided supply.
5. No non-pharmacological treatment targeting OA started or changed during the study.
6. No topical treatment on osteoarthritis index knee during the study.
7. No significant anticoagulant therapy (e.g. Heparin or Lovenox) during the study (treatment such as Aspirin or Plavix is allowed).
8. No systemic treatments that may interfere with safety or efficacy assessments during the study.
9. No immunosuppressants.
10. No use of corticosteroids > 10 mg prednisolone equivalent per day.
 - a. If corticosteroid use is \leq 10 mg prednisolone equivalent per day, and if clinically indicated, subjects should be allowed to decrease their corticosteroid use. Additionally, some subjects may need to increase their steroid dose to treat worsened symptoms in the treated knee, and subjects who increase their corticosteroid dose above their starting dose of corticosteroid during the study will be treated as “treatment failures” for efficacy analysis.
11. No human albumin treatment during the study.

Any medication used during the study should be recorded. All concomitant medication start and stop dates, total daily dose, route and indication should to be recorded.

The only allowed rescue medication is 500 mg of acetaminophen (paracetamol), one tablet every four hours as required by the patient.

8.4 Treatment Compliance

The injection of study drug will be performed by the unblinded injector(s). A 5 mL syringe and 25-gauge needle will be provided. Compliance with treatment is thus assured.

9 ADVERSE EVENTS

9.1 Definition of an adverse event

An adverse event (AE) is defined as any undesired medical occurrence in a patient or clinical investigation patient receiving a pharmaceutical product and which does not necessarily have a causal relationship with this treatment. An AE can therefore be any unfavorable sign or unintended sign (including an abnormal laboratory finding), symptom, or disease temporarily associated with the use of a study drug, whether or not it is related to the study drug.

Assessment of severity of an AE will be rated according to categories listed in [Table 9.1](#) .

Table 9.1 Definitions of AE Severity

Grade 1 (MILD): The symptom is barely noticeable to the study patient and does not influence performance or functioning. Concomitant medication is not ordinarily indicated for relief of mild AEs.
Grade 2 (MODERATE): The symptom is of sufficient severity to make the study patient uncomfortable and to influence performance of daily activities. Concomitant medication may be indicated for relief of moderate AEs.
Grade 3 (SEVERE): The symptom causes severe discomfort, sometimes of such severity that the study patient cannot continue in the study. Daily activities are significantly impaired or prevented by the symptom. Concomitant medication may be indicated for relief of severe AEs.

Determination of the relationship between the AE and the study drug will be made using the guidelines presented in [Table 9.2](#).

Table 9.2 Guidelines for Determining the Relationship (if any) Between Adverse Event and the Study Drug

Unrelated	The adverse event is unlikely to have been caused by study drug.
Possibly related	It is unclear whether the adverse event may have been caused by study drug.
Related	The adverse event is likely to have been caused by study drug.

9.2 Definition of a Serious Adverse Event

A Serious Adverse Event (SAE) is any untoward medical occurrence that occurs at any dose that:

- Results in death
- Is life-threatening (patient is at immediate risk of death from the event as it occurred)
- Requires in-patient hospitalization (formal admission to a hospital for medical reasons) or prolongation of existing hospitalization
- Results in persistent or significant disability/incapacity
- Results in a congenital anomaly/birth defect

Important medical events that may not result in death, are not life-threatening, or do not require hospitalization may be considered SAEs when, based on appropriate medical judgment, they

may jeopardize the patient and may require medical or surgical intervention to prevent one of the outcomes listed in this definition. Examples of such events include allergic bronchospasm requiring intensive treatment in an emergency room or at home, blood dyscrasias or convulsions that do not result in in-patient hospitalization, or the development of drug dependency or drug abuse.

Hospitalizations for elective surgery or other medical procedures that are not related to a treatment-emergent AE are not considered SAEs.

9.3 Recording of adverse events and serious adverse events

Recording and reporting of adverse events should be in accordance with the FDA final “Guidance for Industry and Investigators Safety Reporting Requirements for INDs and BA/BE Studies” of December 2012.

Any AE is to be recorded in the eCRF. In order to avoid vague, ambiguous, or colloquial expressions, the AE should be recorded in standard medical terminology rather than the patient’s own words. Whenever possible, the investigator should combine signs and symptoms that constitute a single diagnosis.

The existence of an AE may be concluded from a spontaneous report of the patient, from the physical examination, or from special tests (e.g. laboratory assessments, where applicable, or other study-specified tests [source of AE]).

The reporting period begins from the time that the patient receives IA injection at the Baseline visit through including patient’s Final Visit at 24 weeks. Any events continuing at study exit will be followed for 30 days or to resolution, or until no improvement is expected, whichever comes first. Any SAE occurring after the reporting period must be promptly reported if a causal relationship to the investigational drug is suspected. If the patient begins a new therapy, the safety reporting period ends at the time the new treatment is started, however, death must always be reported when it occurs during the 24-week study period irrespective of intervening treatment.

Each AE is to be evaluated for duration, severity, seriousness, and causal relationship to the investigational drug. Any action(s) taken, and the outcome must also be recorded.

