10.3.11.4 Safety data

Safety data will be evaluated by changes in vital sign measurements and the frequency and severity of AEs. Concomitant medication will be recorded for safety.

Adverse events:

The Investigator is responsible for monitoring the safety of patients who have enrolled in the study. All AEs considered to be possibly related to Ampion will be followed until the event resolves or stabilized without further change. Patients will be followed for the occurrence of AEs until 12 weeks after the first dose of study medication.

Investigators are required to document all AEs occurring during the clinical trial, commencing with the first day of treatment and including the protocol-defined post-treatment follow-up period on the appropriate CRF pages.

The severity of AEs (mild, moderate, severe), relatedness (related, possibly related, unrelated) along with the duration, action taken, and outcome (e.g., study withdrawal) will also be recorded. In addition, events meeting the criteria of a SAE) must be reported to the Sponsor within 24 hours on the SAE reporting forms.

10.3.11.5 Efficacy data:

All efficacy variables will be assessed at Baseline (Day 0), Week 2 (Day 14 ± 7), Week 4 (Day 30 ± 7), Week 6 (Day 42 ± 7), Week 8 (Day 56 ± 7), Week 10 (Day 70 ± 7) and Week 12 (Day 84 ± 7). For analysis of baseline WOMAC A pain, the baseline pain score is the average of all scores measured during days -7 to 0, prior to injection of treatment. For analysis of week 12 WOMAC A pain, the week 12 pain score is the average of all scores measured during the seven days prior to and including the Week 12 office visit.

All statistical tests will be two-sided, except the co-primary endpoints which require superiority in pain vs. saline control in pain and superiority to baseline in function.

Unless otherwise specified, continuous variables will be summarized with the number of non-missing observations, mean, standard deviation, median, minimum, and maximum displayed. Categorical data will be summarized as counts and percentages. All efficacy assessments will be summarized as the measured value and as the change from Baseline by treatment at each timepoint. Summary statistics will include number of observations, mean, standard deviation, median, minimum and maximum. Change from Baseline will also include a 95% confidence interval.

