## **6. ANALYSIS SUBSETS**

### **6.1 Data Subsets**

#### **6.1.1 Safety Analysis Set**

The safety analysis population is defined as all patients who are randomized and receive study medication (Ampion or saline). Patients will be analyzed as treated. Summaries of data will include all collected data.

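### Protocol 9.3 ends adverse event reporting when an undefined new therapy starts, which understates TEAE incidence and contradicts the protocol's other AE and SAE rules

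*Protocol*

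**What the plan says.** **Protocol 9.3** starts the clock at injection ("The reporting period begins from the time that the patient receives IA injection at the Baseline visit") and runs it through the final visit at 24 weeks. Three further rules shape the period:

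- The cut-off: "If the patient begins a new therapy, the safety reporting period ends at the time the new treatment is started".
- An exception in the same sentence: "death must always be reported when it occurs during the 24-week study period irrespective of intervening treatment".
- A second exception in the sentence just before it: "Any SAE occurring after the reporting period must be promptly reported if a causal relationship to the investigational drug is suspected".

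Neither document says what counts as a new therapy.

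**Protocol 10.3.11.4** carries no such cut-off ("Investigators are required to document all AEs occurring during the clinical trial, commencing with the first day of treatment"), but it gives a different length of follow-up: "Patients will be followed for the occurrence of AEs until 12 weeks after the first dose of study medication".

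**SAP.** The Safety set is all randomised patients who received study medication, and for it "Summaries of data will include all collected data". Section 8.5 summarises AEs as numbers of patients by treatment group and states no adjustment for time at risk. TEAE incidence and severity is a listed secondary endpoint. The protocol synopsis says it will not be tested statistically.

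**The concern.** Study treatment is a single injection, so starting another therapy does not end exposure to it. A patient who starts one is not withdrawn for that reason under Protocol 7.2, keeps attending visits and stays in the AE denominators. Under 9.3, only the numerator stops accumulating.

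The trigger is also unlikely to be unrelated to outcome. Protocol 10.3.11.3 defines treatment failure as added medication or surgery for worsened symptoms in the treated knee, and both documents compare failures between arms. Where the new therapy is of that kind, AE recording stops at a post-randomisation event that depends on response.

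At stake are the completeness of a secondary safety endpoint and the Safety Monitoring Committee's view of events. Protocol 7.1 lists induction of autoimmune arthritis, if possibly related, as a reason to suspend the study. A case that did not meet seriousness criteria and arose after a new knee therapy would fall outside the reporting period in 9.3.

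**Working it through.** **1. What the cut-off removes.** Taking 9.3 as a whole, for events after a new therapy starts:

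| Event | Still reported under 9.3? |
|---|---|
| Death within 24 weeks | Yes |
| Non-fatal SAE, drug relationship suspected | Yes |
| Non-fatal SAE, drug relationship not suspected | No |
| Non-serious AE, related or not | No |

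**2. Whether other sections agree.**

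| Place | Rule | Cut at new therapy? |
|---|---|---|
| Protocol 9.3.1 | All AEs during the study are followed up | No |
| Protocol 9.4.1 | All SAEs go into the eCRF within 24 hours of first knowledge | No |
| Protocol 10.3.11.4 | All AEs during the trial are documented; also a 12-week window | No |
| SAP 5.2, TEAE definition | Any AE starting or worsening after dosing, no end date | No |
| Protocol Table 6.1, SAP 13 | AEs at every post-injection contact except the pre-Week 12 reminder call, through Week 24 | No |

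The cut-off appears only in 9.3. SAP 6.1.1 does not contradict it: that section summarises whatever was collected, so differences in what sites collect pass straight into the tables.

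**3. Size.** The documents give no rate of starting new therapy, so there is no figure to reproduce. Everything below is an illustration on assumed rates.

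*Follow-up lost, all starts at Week 8.* Share lost = p × (24 − 8)/24 = 0.667p.

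- p = 10%: 6.7%
- p = 15%: 10.0%
- p = 20%: 13.3%

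On the 12-week window of 10.3.11.4, the factor is (12 − 8)/12 = 0.333, giving 3.3%, 5.0% and 6.7%.

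*Mean follow-up, starts uniform over 24 weeks.* Mean weeks = 24 − 12p.

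- 10% in both arms: 22.8 and 22.8, no imbalance
- 20% and 10%: 21.6 and 22.8
- 40% and 20%: 19.2 and 21.6, that is 80% and 90% of the planned 24 weeks

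*Effect on the planned summary, patients with at least one AE.* Assume a true 24-week incidence of 38% in both arms (between the 35.4% and 41.5% in Protocol Table 1.3, overall population), a constant hazard, and truncation at Week 8.

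- Incidence by Week 8 = 1 − 0.62^(8/24) = 14.7%
- Loss per truncated patient = 38.0 − 14.7 = 23.3 points
- Recorded incidence: 38.0 − 0.10 × 23.3 = 35.7% at p = 10%; 34.5% at 15%; 33.3% at 20%
- Spurious gap: about 1.2 points for 10% against 15%, and 2.3 points for 10% against 20%

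Using 35.4% or 41.5% instead of 38% moves the larger gap only to 2.2 or 2.5 points.

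*SAEs.* With an assumed 2% risk, 0.02 × 517 = 10.3 are expected per arm. The 40% and 20% case would record 10.3 × 0.80 = 8.3 and 10.3 × 0.90 = 9.3. This overstates the loss, because the two exceptions in 9.3 keep some of these events.

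**The case against.** **Much of the safety signal is protected.** A reader might infer that every serious event other than death is lost. The documents do not support that: the sentence before the cut-off keeps SAEs suspected to be drug-related, and 9.4.1 and 10.3.11.4 ask for SAEs within 24 hours without exception. This stands. What remains exposed is non-fatal SAEs not suspected to be related, and all non-serious AEs. For SAEs, a case-by-case causality judgement then decides what enters the comparison.

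**Unequal follow-up is not documented.** A reader might also infer that the rule does cut the arms unequally, or flatters Ampion. Neither follows. Imbalance needs different rates of starting new therapy, and none are given. If Ampion works, saline patients would be expected to start new therapy more often and lose more follow-up, so Ampion would look relatively worse on AE counts. This stands, though equal truncation would still understate incidence in both arms.

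**The mechanism depends on how the term is read.** If new therapy means any drug for any reason, much of the truncation is unrelated to response. If it means treatment of a worse knee, its scope is narrower. This is fair, and it is why the undefined term is part of the defect. The broad reading truncates more patients: Protocol Table 9.1 allows concomitant medication for moderate and severe AEs, so treating one AE could end recording of the next. The narrow reading makes the truncation response-related.

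**Data may be collected anyway.** The visit schedule asks about AEs through Week 24, so sites may ignore the cut-off. That is possible, but then capture depends on which section a site follows.

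**Conclusion.** The point holds in this form. Where 9.3 is followed, TEAE incidence is understated after a new therapy starts, for non-serious AEs and for non-fatal SAEs not suspected to be drug-related, with no matching change to the denominator. A difference between arms is a plausible risk, not an established fact. On the assumed rates above it is in the order of one to two and a half percentage points for patients with any AE, and zero if the arms start new therapy equally. TEAEs are descriptive, so neither the Type I error nor the efficacy conclusions are touched.

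The internal contradiction needs no assumption: 9.3 cannot be applied together with 9.3.1, 9.4.1, 10.3.11.4 and the visit schedule as written. The separate 12-week window in 10.3.11.4 means that the reporting period is unsettled even for patients who never start a new therapy.

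**What to change.** 1. Delete the new-therapy cut-off from Protocol 9.3.
2. Reconcile the 12-week follow-up in 10.3.11.4 with the 24-week period in 9.3, so that one stated AE and SAE reporting period applies to every treated patient. Removing the cut-off alone would leave this conflict in place.
3. Align 9.3.1, 9.4.1 and the SAP's TEAE definition with that period, including an explicit end date.
4. Define new therapy and add an eCRF flag for events that start after it.
5. In the SAP, tabulate all events as the main summary, with a supplementary table that stops at the start of new therapy.

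The cost is a short protocol amendment, matching SAP wording, one eCRF flag and one extra table. No visits are added, because AEs are already scheduled through Week 24. The downside is that some events caused by the new therapy will be counted. The flag and the supplementary table let a reader separate them.
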